8.4.7 Events of Clinical Interest

Selected serious and nonserious AEs are also known as ECIs and must be reported to the Sponsor.

Events of clinical interest for this study include:

- An overdose of Sponsor's product, as defined in Section 8.5.
- An elevated AST or ALT laboratory value that is greater than or equal to 3X the ULN and an elevated total bilirubin laboratory value that is greater than or equal to 2X the ULN and, at the same time, an alkaline phosphatase laboratory value that is less than 2X the ULN, as determined by way of protocol-specified laboratory testing or unscheduled laboratory testing.*

*Note: These criteria are based on available regulatory guidance documents. The purpose of the criteria is to specify a threshold of abnormal hepatic tests that may require an additional evaluation for an underlying etiology. The study-site guidance for assessment and follow up of these criteria can be found in the Investigator Study File Binder (or equivalent).

8.5 Treatment of Overdose

For purposes of this study, an overdose will be defined as any dose exceeding the prescribed dose for MK-7684A by 3 times (ie, 300%). No specific information is available on the treatment of overdose of MK-7684A. In the event of overdose, MK-7684A should be discontinued and the participant should be observed closely for signs of toxicity. Appropriate supportive treatment should be provided if clinically indicated.

8.6 Pharmacokinetics

To further evaluate immunogenicity and exposure in this indication, and also to evaluate exposure of the proposed dosing regimen, sample collections for analysis of ADA and PK are currently planned for investigational agents as shown in the SoA (Section 1.3). Blood samples will be obtained to measure PK of investigational agents in the serum. If ongoing ADA and/or PK results continue to be consistent with existing ADA and/or PK data from other clinical studies with these investigational agents, it may be decided to discontinue or reduce further sample collection in this study.

Based on PK data obtained in this study as well as PK data obtained from other studies, a population PK analysis may be performed to characterize PK parameters (CL, V) and evaluate the effect of extrinsic and intrinsic factors to support proposed dosing regimen. PK

data may also be used to explore the E-R relationships for antitumor activity/efficacy as well as safety in the proposed patient population, if feasible. The results of these analyses, if performed, will be reported separately.

Protocol Amendment 04 implementation: PK and ADA sampling will no longer be collected for any participants.

8.6.1 Blood Collection for PK

Sample collection, storage, and shipment instructions for serum samples will be provided in the Laboratory Manual. PK samples should be drawn according to the PK collection schedule in the SoA (Section 1.3).

8.6.2 Blood Collection for Anti-drug Antibodies

Sample collection, storage, and shipment instructions for serum samples will be provided in the Laboratory Manual. Anti-drug antibody samples should be drawn according to the ADA collection schedule in the SoA (Section 1.3). Simultaneous PK sampling is required for interpretation of ADA analysis.

8.7 Pharmacodynamics

Pharmacodynamic parameters will not be evaluated in this study.

8.8 Biomarkers

To identify novel biomarkers, the following biospecimens to support exploratory analyses of cellular components (eg, protein, RNA, DNA, metabolites) and other circulating molecules will be collected from all participants as specified in the SoA:

- Blood for genetic analysis
- Blood for ctDNA analysis
- Tumor tissue

Sample collection, storage, and shipment instructions for the exploratory biomarker specimens will be in the Laboratory Manual. Please refer to Appendix 7 for country-specific requirements.

Protocol Amendment 04 implementation: Biomarker samples will no longer be collected for any participants.

8.8.1 Planned Genetic Analysis Sample Collection

The planned genetic analysis sample should be drawn for planned analysis of the association between genetic variants in DNA and drug response. This sample will not be collected at the site if there is either a local law or regulation prohibiting collection, or if the IRB/IEC does

not approve the collection of the sample for these purposes. If the sample is collected, leftover extracted DNA will be stored for FBR if the participant provides documented informed consent for FBR. If the planned genetic analysis is not approved, but FBR is approved and consent is given, this sample will be collected for the purpose of FBR.

The planned genetic analysis sample should be obtained pre-dose on Day 1 but may be collected at the next scheduled blood draw, if needed. Sample collection, storage, and shipment instructions for planned genetic analysis samples will be in the Operations/Laboratory Manual.

Please refer to Appendix 7 for country-specific requirements.

8.9 Future Biomedical Research Sample Collection

If the participant provides documented informed consent for FBR, the following specimens will be obtained as part of FBR:

• Leftover samples listed in Section 8.8, Biomarkers (including any extracted material from samples)

8.10 Medical Resource Utilization and Health Economics

All-cause hospitalizations and emergency room visits must be reported in the eCRF, from the time of treatment randomization through 90 days after cessation of study intervention, or 30 days after cessation of study intervention, if the participant initiates new anticancer therapy, whichever is earlier.

Medical resource utilization and health economics associated with medical encounters will be collected in the eCRF by the investigator and study-site personnel for all participants throughout the study. Protocol-mandated procedures, tests, and encounters are excluded.

8.11 Visit Requirements

Visit requirements are outlined in Section 1.3. Specific procedure-related details are provided in Section 8.

8.11.1 Screening

Documented informed consent must be provided before performing any protocol-specific procedure. Results of a test performed before the participant signing consent as part of routine clinical management are acceptable in lieu of a screening test if performed within the specified time frame.

Confidential

Screening procedures are to be completed within 28 days before the first dose of study intervention.

Participants may be rescreened after initially failing to meet the inclusion/exclusion criteria. Results from assessments during the initial screening period are acceptable in lieu of a repeat screening test if performed within the specified time frame and the corresponding inclusion/exclusion criteria is met. Participants who are rescreened will retain their original screening number.

8.11.2 Treatment Period/Vaccination Visit

Visit requirements are outlined in the SoA (Section 1.3). Specific procedure-related details are provided in Section 8.1.

8.11.3 Participants Discontinued From Study Intervention but Continuing to be Monitored in the Study

Participants who discontinue study intervention will continue to be monitored for Efficacy and Survival Follow-up as described in Section 8.11.4.

Protocol Amendment 04 implementation: The final visit in the study will be the safety follow-up visit. No further monitoring for efficacy and survival follow-up is required.

8.11.4 Posttreatment Visit

8.11.4.1 Safety Follow-up Visit

The mandatory Safety Follow-up Visit should be conducted approximately 30 days after the last dose of study intervention or before initiation of a new anticancer treatment, whichever comes first.

Protocol Amendment 04 implementation: Safety follow-up visit will be the final visit in the study.

8.11.4.2 Efficacy Follow-up Visits

Participants who complete the protocol-required cycles of study intervention or who discontinue study intervention for a reason other than disease progression will begin Efficacy Follow-up and should be assessed per the protocol-defined schedule (SoA, Section 1.3) to monitor disease status. Every effort should be made to collect information regarding disease status until the start of new anticancer therapy, disease progression, withdrawal of consent, death, or end of study. Information regarding poststudy anticancer treatment will be collected if new treatment is initiated. Participants who completed all efficacy assessments and/or will not have further efficacy assessments must enter Survival Follow-up.

Protocol Amendment 04 implementation: Efficacy follow-up visits are not required. Participants currently on study treatment will have the safety follow-up visit as the final visit. Participants currently in efficacy follow-up are considered to have completed the study and should obtain imaging and further oncological care as per local standard of care.

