	After the end of treatment, each participant will be followed for the occurrence of adverse events and spontaneously reported pregnancy.
	Participants who discontinue for reasons other than radiographic disease progression will have posttreatment follow-up imaging for disease status until any of the conditions for discontinuation of imaging are met.

All participants will be followed for overall survival until death, withdrawal of consent, or the end of the study.
Protocol Amendment 04 implementation: There will be no collection of efficacy data including tumor scans, vital status, and post-treatment anticancer therapy status.

Study Governance Committees:

Executive Oversight Committee	Yes
Data Monitoring Committee	Yes
Clinical Adjudication Committee	No

Study governance considerations are outlined in Appendix 1.

Study Accepts Healthy Participants: No

A list of abbreviations is in Appendix 8.

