Vital Status			Х	After verified disease progression or start of new anticancer treatment. In addition, upon Sponsor request, participants may be contacted for vital status at any time during the course of the study.
Tumor Scan				Scans should follow calendar days from randomization and should not be adjusted for dose delays or cycle starts. Unscheduled scans can be performed as clinically indicated. Scans must be submitted and reviewed by BICR. See Section 8.2 for full details.
CT/MRI of chest, abdomen, and pelvis		Х		Use the same imaging modality for all evaluations.
Bone Scan		Х		On-study bone scans should be acquired as clinically indicated or to confirm a CR when bone metastases were present at Screening.
Brain Scan		X		For participants without brain metastases at Screening, on- study brain scans are required at Q12W (84 days \pm 7 days) through Week 48 and then Q24W (168 days \pm 7 days) through Week 96 or more often as clinically indicated. For participants with brain metastases present at Screening, on-study brain scans are to be acquired at all scheduled post-baseline imaging timepoints, or more often as clinically indicated, and to confirm a CR.
Safety Procedures				
Directed Physical Examination	Х			
Vital Signs	Х	1	1	DBP, SBP, heart rate, RR, temperature, pulse oximetry

Study Period:		Posttreatment Follow-	սթ	Notes
Treatment Cycle:	Safety Follow-up	Efficacy Follow-up	Survival Follow-up	
Day (in Cycle)	30 days from last dose (+7 days)	Per imaging schedule	Every 12 weeks (±7 days)	
Audiometry	Х			To be performed if this is the local standard of care only when cisplatin is chosen as the platinum agent. May be performed more often as clinically indicated.
ECOG Performance Status	X			
Thyroid Function Tests (TSH, T3, free T4)	Х			
Hematology	Х			
Chemistry	Х			
AE/SAE review	Х			Record all AEs occurring within 30 days after last dose of study intervention. Record all SAEs occurring up to 90 days after last dose of study intervention or 30 days after last dose of study intervention if the participant initiates new anticancer therapy, whichever comes first. Any treatment-related SAEs must be reported regardless of time they occur.
Patient-Reported Outcomes				As of Amendment 04, PROs will no longer be collected on any participants.
EORTC QLQ-C30	X			
EORTC QLQ-LC13	X			
EQ-5D-5L	X			

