All scheduled scans for participants will be submitted to the iCRO. In addition, a scan that is obtained at an unscheduled time point, for any reason (including suspicion of progression or other clinical reason), should also be submitted to the iCRO if it shows disease progression, or if it is used to support a response assessment. All scans acquired within the protocol-specified window of time around a scheduled scan visit are to be classified as pertaining to that visit.

When the investigator identifies disease progression, the iCRO will verify this progression and e-mail the results to the study site and Sponsor (see Section 8.2.1.4 and Figure 3). In

clinically stable participants, scans are to continue until disease progression has been verified by BICR. If investigator-assessed progression was not verified by BICR, each subsequent scan must be submitted to the iCRO. Once progression is verified by BICR, subsequent scans (if acquired) should not be submitted to the iCRO.

Protocol Amendment 04 implementation: Participants currently on study treatment will have tumor imaging assessed locally based on site's standard of care imaging schedule. Participants currently in efficacy follow-up are considered to have completed the study and therefore should obtain imaging as per local standard of care. BICR verification of progression is no longer applicable.

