8.2.1.2 Tumor Scans During the Study

The first on-study scan should be performed at 6 weeks (42 days \pm 7 days) from the date of randomization. Subsequent tumor scans should be performed every 6 weeks (42 days \pm 7 days) or more frequently if clinically indicated. After 48 weeks (336 days \pm 7 days), participants who remain on treatment will have scans performed every 9 weeks (63 days \pm 7 days). Scan timing should follow calendar days and should not be adjusted for delays in cycle starts.

Scans are to be performed until disease progression is identified by the investigator and verified by BICR, or notification by the Sponsor, or until any of these conditions are met:

- the start of new anticancer treatment
- pregnancy
- death
- withdrawal of consent
- the end of the study

Objective response should be confirmed by a repeat scan performed at least 4 weeks after the first indication of a response is observed. Participants will then return to the regular scan schedule, starting with the next scheduled time point. Participants who receive additional scans for confirmation do not need to undergo the next scheduled scan if it is fewer than 4 weeks later; scans may resume at the subsequent scheduled time point.

Refer to the SoA (Section 1.3) for on-study brain and bone scan requirements.

Protocol Amendment 04 implementation: Participants currently on study treatment will have tumor imaging assessed locally based on site's standard of care imaging schedule. Participants currently in efficacy follow-up are considered to have completed the study and therefore should obtain imaging as per local standard of care. BICR verification of progression is no longer applicable.

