8.2.1.3 End-of-treatment and Follow-up Tumor Scans

If participants discontinue study intervention, tumor scans should be performed at the time of discontinuation (\pm 4-week window) unless previous scans were obtained within 4 weeks of discontinuation. If participants discontinue study intervention due to documented disease progression, this is the final required tumor scan.

If participants discontinue study intervention without documented disease progression, every effort is to be made to monitor disease status by acquiring tumor scans using the same schedule calculated from the date of randomization, refer to Section 8.2.1.2.

Scans are to be continued until one of the following conditions are met:

- disease progression as defined by RECIST 1.1 verified by BICR
- the start of a new anticancer treatment
- pregnancy
- death
- withdrawal of consent
- the end of the study

Protocol Amendment 04 implementation: Participants currently on study treatment will have tumor imaging assessed locally based on site's standard of care imaging schedule. Participants currently in efficacy follow-up are considered to have completed the study and therefore should obtain imaging as per local standard of care. BICR verification of progression is no longer applicable

8.2.1.4 **RECIST 1.1 Assessment of Disease**

RECIST 1.1 will be used as the primary measure for assessment of tumor response, date of disease progression, and as a basis for all protocol guidelines related to disease status (eg, discontinuation of study intervention). Although RECIST 1.1 references a maximum of 5 target lesions in total and 2 per organ, this protocol allows a maximum of 10 target lesions in total and 5 per organ, if clinically relevant to enable a broader sampling of tumor burden.

Upon investigator-assessed disease progression, the indicative scan is to be submitted immediately to iCRO for BICR verification of progression. After submission of scan(s), the iCRO will e-mail the assessment to the site and Sponsor.

Protocol Amendment 04 implementation: Participants currently on study treatment will have tumor imaging assessed locally based on site's standard of care imaging schedule. No need to submit scans to iCRO, and VOP request and central review of imaging will no longer be applicable.

If disease progression is not verified, the process continues as follows:

- If participant is clinically stable, continue study intervention per protocol

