 - - Resume imaging per protocol schedule (\geq 4 weeks to next scan)
 - - Send scans to iCRO
 - - Continue local assessment
 - - Do not change investigator assessment of progression
 - If subsequent scan(s) indicate progression, submit scan(s) to iCRO to request verification
- If the participant is not clinically stable, best medical practice is to be applied

Before stopping study intervention or imaging or starting new anticancer therapy in a participant who is clinically stable, communication with the Sponsor is required.

If disease progression is verified, the process continues as follows:

- Investigator judgment will determine action
- If the participant is clinically stable and study intervention is to continue, communication with the Sponsor is required and a reconsent addendum must be signed
- Obtain scans locally per original protocol schedule
- Do not send scans to iCRO

Figure 3 illustrates the study intervention decision process involving verification of disease progression for participants.

- For this decision process, lack of clinical stability is defined as:
 - - Unacceptable toxicity
 - - Clinical signs or symptoms indicating clinically significant disease progression
 - - Decline in performance status
 - Rapid disease progression or threat to vital organs or critical anatomical sites (eg, CNS metastasis, respiratory failure due to tumor compression, spinal cord compression) requiring urgent alternative medical intervention

Figure 3 Study Intervention Decision-Making Process

Study Intervention Decision Making Process When Progression per RECIST 1.1 is Observed by Investigator (PFS endpoint)

iCRO=imaging Contract Research Organization; VOP=verification of progression

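### Do the differing imaging stop rules for progression that central review did not verify undermine the BICR-assessed PFS?

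*Combined protocol and SAP*

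**What the plan says.** Section 8.2.1.2 sets the on-study rule: "Scans are to be performed until disease progression is identified by the investigator and verified by BICR". The same sentence adds notification by the Sponsor as another endpoint.

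Section 8.2.1.3 covers scans after treatment stops. Its opening paragraph reads: "If participants discontinue study intervention due to documented disease progression, this is the final required tumor scan". Its own list of stopping conditions then gives "disease progression as defined by RECIST 1.1 verified by BICR".

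Section 8.2.1 ties the requirement to condition: in "clinically stable participants, scans are to continue until disease progression has been verified by BICR". Section 8.2.1.4 has a procedure for unverified progression. Stable participants stay on treatment and imaging, and their scans still go to the imaging vendor. For the others it says only: "If the participant is not clinically stable, best medical practice is to be applied".

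Two summary texts name no assessor. Section 8.11.4.2 admits to Efficacy Follow-up those who "discontinue study intervention for a reason other than disease progression will begin Efficacy Follow-up". The Synopsis says: "Participants who discontinue for reasons other than radiographic disease progression will have posttreatment follow-up imaging for disease status". The Schedule of Activities (Section 1.3) places vital-status contacts as follows: "After verified disease progression or start of new anticancer treatment".

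Section 9.4.1 defines a PFS event as BICR progression or death. The content of Table 11, the PFS censoring rules, is redacted; its title covers primary and sensitivity analyses.

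**The concern.** Read literally, a participant who stops treatment because the investigator sees progression, while BICR does not, could be handled in different ways. Section 8.2.1.2 and the list in Section 8.2.1.3 keep that participant on scans. The first paragraph of Section 8.2.1.3, Section 8.11.4.2 and the Synopsis can be read as releasing them. Section 7.1 lists any progression separately from radiographic progression as a reason to stop treatment, which widens the second reading.

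Participants who leave imaging at this point are probably close to a true BICR event. If they are censored at their last scan, the censoring is plausibly informative. If they are counted at death, the event is dated late. Either way PFS reads too high, and if more participants leave in one arm the hazard ratio is biased. PFS carries hypothesis H2, so the question is a fair one.

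**Working it through.** **Step 1: how many rules are there?** Two passages truly conflict: the opening paragraph of Section 8.2.1.3 on one side, its list together with Section 8.2.1.2 on the other. The remaining texts do not add a further rule. Section 8.11.4.2 and the Synopsis leave the assessor unnamed. Section 8.11.4.2 refers to the Schedule of Activities, whose tumor-scan row requires BICR review and sends the reader to Section 8.2 for details. Sections 8.2.1 and 8.2.1.4 qualify the verification rule by clinical stability; they do not contradict it.

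**Step 2: who is exposed?**
- Stable and unverified: covered by Section 8.2.1.4, which also requires contact with the Sponsor before treatment or imaging stops or new therapy starts.
- Starts new anticancer therapy, or dies: imaging ends under Sections 8.2.1.2, 8.2.1.3 and 8.11.4.2 alike, so there is no conflict.
- Left over: mainly unverified, clinically unstable participants who start no new therapy. Section 8.11.4.3 keeps those who do not enter Efficacy Follow-up in survival follow-up, and Section 9.6.1.2 treats death as a PFS event.

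**Step 3: what could it do to the hazard ratio?** The documents give no exposure rate, so the shares here are assumptions. If 10% to 25% of local progressions are unverified and 20% to 50% of those leave imaging, the exposed share runs from 0.10 × 0.20 = 2% to 0.25 × 0.50 = 12.5%.

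A simulation used exponential PFS with a control median of 5.2 months (from the atezolizumab trial in Section 2.2.1.1), the protocol's scan schedule (every 6 weeks to week 48, then every 9 weeks), 10% of first events as deaths (assumed), and uniform follow-up of 8 to 26 months (assumed). Exposed participants had no scan after a local call made one scan early. With equal exposure in both arms:
- the hazard ratio without loss, 0.798, becomes 0.796 to 0.799;
- the hazard ratio without loss, 1.094, becomes 1.093 to 1.097.

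The largest shift is 1.097 − 1.094 = 0.003.

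A hand calculation shows why. Let m be the mean PFS, l the lead time of one scan interval (6 weeks, about 1.4 months) and f the share of events lost. The observed event rate is about (1 − f)/(m − f·l), with m = 5.2/ln 2 = 7.50 months. If both arms have the same true rate and the same f, the ratio is exactly 1. Only a difference between arms matters:
- f = 0.10: 0.90/(7.50 − 0.14) = 0.1223
- f = 0.05: 0.95/(7.50 − 0.07) = 0.1279
- ratio: 0.1223/0.1279 = 0.96

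A separate simulation that stops follow-up at 18 months gives 0.95 for this case. In the first simulation, an assumed exposure of 3% against 6%, with the lost participants censored, moves 0.80 to 0.78 or 0.81. The documents show no imbalance, and investigators were blinded until the interim decision.

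**Step 4: what about the PFS curves themselves?** They would read somewhat high in both arms, but the model cannot say by how much. With a 5.2-month median, exponential PFS is 2^(−6/5.2) = 44.9% at 6 months and 2^(−9/5.2) = 30.1% at 9 months. Section 2.2.1.2 reports 34.1% and 17.2% for pembrolizumab plus the same chemotherapy in another trial. The model declines too slowly for its absolute levels to be relied on, so only the hazard-ratio result is used here.

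**Step 5: what is still open?** Amendment 04 ended efficacy follow-up and BICR verification. Section 9 cancels the final analysis and rules out efficacy analyses of data collected after the 04-JUN-2024 cutoff.

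**The case for a change.** The strongest reply is that the conflict inside Section 8.2.1.3 is real, that the Sponsor-contact safeguard covers only clinically stable participants, and that PFS up to the cutoff can still be reported. A by-arm count of participants with no scan after an unverified local progression would show whether the arms differ. Section 9.6.1.4 provides a summary of censoring reasons for DOR, and no visible text does so for PFS. Investigator-assessed PFS, an exploratory endpoint in Section 3, re-dates progression for everyone and so does not isolate this group.

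The first part stands: the passages should have been reconciled while they were in force. The rest is a reporting preference. Tables 11 and 13 are redacted where they deal with PFS censoring, so a count or sensitivity analysis of this kind may already be planned; redacted text cannot be treated as absent. Nor is any scan shown to have been lost because of the wording. In a clinically failing patient, missed imaging may simply reflect the patient's condition.

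**Conclusion.** This is a wording inconsistency in text that no longer governs any imaging, and no change to the plan follows. Section 8.2.1.4 handles the main case, the other sections point back to Section 8.2, and the remaining group is narrow and of unknown size. With exposure equal between arms and up to 12.5% of local progressions, the PFS hazard ratio moves by at most 0.003; a material bias needs an imbalance for which there is no evidence. That result rests on the assumed exposure shares and on exponential PFS. How these participants enter the PFS analysis cannot be seen, because Table 11 is redacted. The primary endpoint, OS, and the futility decision do not use scan data. A by-arm list of PFS censoring reasons up to the cutoff would be a helpful courtesy in the report if it is not already planned, but no shown result or conclusion depends on it.
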